5.1 Eligibility

5.1.1 Inclusion criteria

- Patients with progressive, locally recurrent, or metastatic osteosarcoma (i.e. high-risk only) with no standard curative options available with at least one indicator lesion avid on ^{99m}Tc -MDP scan or a Sodium Fluoride (Na F) Bone PET scan will be eligible. In addition, subjects with extremely rare bone forming osteosarcoma-like tumors that behave like osteosarcoma phenotypically and are clinically treated like osteosarcoma (eg. Malignant Fibrous Histiocytoma of Bone or malignant transformation of giant cell tumor of bone) may be included if they satisfy all of the inclusion criteria.
- Anatomic imaging (CT or MRI) of all sites of disease along with chest CT at baseline and restaging for all patients will be done to allow for assessment of RECIST progression. RECIST progression will determine progressive disease regardless of other imaging.
- Indicator lesion that has uptake of ^{99m}Tc -MDP on bone scan or a Sodium Fluoride (Na F) Bone PET scan and can be subjected to quantitative assessment by this scans and possibly other means
 - Age 15 and above and >40 kg.
 - ECOG=2 or better
 - Subjects or their guardians must be able to understand and be willing to sign the written informed consent form. A signed informed consent form must be appropriately obtained prior to the conduct of any trial-specific procedure.
 - All acute toxic effects of any prior treatment have resolved to NCI-CTCAE v4.0 Grade 1 or less at the time of signing the Informed Consent Form (ICF).
 - Women of childbearing potential must have a negative serum or urine pregnancy test performed within 7 days prior to the start of study drug. Post-menopausal women (defined as no menses for at least 1 year) and surgically sterilized women are not required to undergo a pregnancy test.
 - Subjects (men and women) of childbearing potential must agree to use adequate contraception beginning at the signing of the ICF until at least 30 days after the last dose of study drug. The definition of adequate

contraception will be based on the judgment of the principal investigator or a designated associate.

- Acceptable hematology and serum biochemistry screening values:
 - White Blood Cell Count (WBC) \geq 1500/mm³
 - Absolute Neutrophil Count (ANC) \geq 1,000/mm³
 - Platelet (PLT) count \geq 75,000/mm³
 - Hemoglobin (HGB) \geq 8 g/dl
 - Total bilirubin level \leq 1.5 x institutional upper limit of normal (ULN)
 - Aspartate aminotransferase (AST) and alanine aminotransferase (ALT) \leq 2.5 x ULN
 - Creatinine \leq 1.5 x ULN
 - Albumin > 25 g/L
- Willing and able to comply with the protocol, including follow-up visits and examinations

5.1.2 Exclusion criteria

- Diagnosis other than osteosarcoma
- ^{99m}Tc-MDP bone scan with no significant uptake (i.e. “nothing” for a bone-seeking isotope to target/ i.e. indicator lesion that would be expected to have the bone-seeking targeted uptake of 223-radium dichloride)
- Other malignancy treated within the last 3 years (except non-melanoma skin cancer or low-grade superficial bladder cancer)
- Any other serious illness or medical condition, such as but not limited to:
 - Any active infection \geq National Cancer Institute Common Terminology Criteria for Adverse Events (NCI-CTCAE) version 4.03 Grade 2
 - Cardiac failure New York Heart Association (NYHA) III or IV
 - Fecal incontinence (this is because of Ra-223 elimination in feces)
- Women who are pregnant or breast-feeding.
- Inability to comply with the protocol and/or not willing or not available for follow-up assessments.

- Any condition which, in the investigator's opinion, makes the subject unsuitable for trial participation.
- Concurrent anti-cancer therapy (chemotherapy, radiation therapy, surgery, immunotherapy, biologic therapy, or tumor embolization)
- Patients on oxygen

5.2 Withdrawal of subjects from study

5.2.1 Withdrawal

Subjects **must be withdrawn from the trial** (treatment and procedures) for the following reasons:

- Subject withdraws consent from study treatment and study procedures. A subject must be removed from the trial at his/her own request or at the request of his/her legally acceptable representative. At any time during the trial and without giving reasons, a subject may decline to participate further. The subject will not suffer any disadvantage as a result.
- Progressive disease and dose limiting toxicity (DLT)
- Subject is lost to follow-up.
- Death.

Subjects **may be** withdrawn from the study for the following reasons:

- The subject is non-compliant with study drug, trial procedures, or both; including the use of anti-cancer therapy not prescribed by the study protocol.
- Pregnancy. Pregnancy will be reported as an SAE. (Note: subjects who have been withdrawn from treatment with study drug because of pregnancy should not undergo CT scans [with contrast]/MRI or bone scans while pregnant.)
- If, in the investigator's opinion, continuation of the trial would be harmful to the subject's well-being.
- The development of a second cancer.
- Development of an intercurrent illness or situation which would, in the judgment of the investigator, significantly affect assessments of clinical status and trial endpoints.

- Deterioration of ECOG performance status to 4.
- Use of illicit drugs or other substances that may, in the opinion of the investigator, have a reasonable chance of contributing to toxicity or otherwise skewing trial result.

Any subject removed from the trial will remain under medical supervision until discharge or transfer is medically acceptable.

In all cases, the reason for withdrawal must be recorded in the CRF and in the subject's medical records.

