Most common non-hematologic all grades adverse events occurring in more than 15% of patients were: bone pain (43% vs. 58%), diarrhea (22% vs. 13%), nausea (34% vs. 31%), vomiting (17% vs. 13%) and constipation (18% vs. 18%). Most common hematologic all grades adverse events were anemia (27% vs. 27%), neutropenia (4% vs. 1%) and platelets (8% vs. 6%).

Subgroup survival analysis

Subgroup survival analysis showed a consistent survival benefit for treatment with Ra-223 dichloride, independent of total alkaline phosphatase (ALP), current use of bisphosphonates, prior use of docetaxel and baseline ECOG status.

Pain relief

The results from the phase III ALSYMCA study regarding time to external beam radiation therapy (EBRT) for pain relief and fewer patients reporting bone pain as an adverse event in the Ra-223 dichloride group indicate a positive effect on bone pain. This is further supported by the effects seen on bone pain using specific pain measures in a single dose Phase II study.

2. Study objectives

- 2.1** Primary Objective: Determine maximum tolerated or recommended dose of monthly Ra-223 dichloride in patients with recurrent or metastatic osteosarcoma. Comparison of safety and toxicity of 50, 75, and 100 kBq Ra-223- dichloride /kg will be made.
- 2.2** Secondary Objectives: compare alkaline phosphatase reduction to quantitative imaging techniques (^{99m}Tc -MDP, ^{18}F FDG-PET-CT, ^{18}F Na PET-CT scans to determine objective response of osteosarcoma indicator lesions to 223-radium dichloride

3. Investigator[s] and other study participants

PI

[name] MD
MDACC Assistant Professor,
Investigational Cancer Therapeutics, [name]
[contact]; [contact]
[contact]

Co- PI and Ra-223 dichloride license holder: [name] MD
MDACC Associate Professor [name]
[name]; [contact] [contact]
[contact]

Other key personnel: [name] Senior Medical Physicist
[name] [contact]; [contact]
[contact]

[name], Professor, Biostatistics [contact]. [name]
[contact]

[figure not shown]
4. Study design

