beforehand and given suitable personal protection equipment (i.e. universal blood and body fluid precautions - especially when handling ashes containing potentially radioactive bone fragments. Calculations and the rationale for radiation dose estimates are available upon request (see investigators Brochure).

Definition of Dose-Limiting Toxicities (DLTs):

Toxicities will be graded in severity according to the guidelines outlined in the NCI Common Terminology Criteria for Adverse Events (CTCAE) version 4.0 (publish date 28-May-2009). Dose-limiting toxicities include all adverse experiences that are related to study medication, and clearly not related to disease progression or intercurrent illness.

Based on prior experience with other bone seeking radiopharmaceuticals and Ra-223 dichloride in prostate cancer patients, the expected dose limiting toxicity (DLT) will be hematologic. Lymphopenia is common in patients with bone metastases and will be monitored, but not considered a DLT in this protocol. Any grade 4 anemia, any grade 4 neutropenia for >7 days or grade 4 neutropenia with fever (a single temperature greater than 38.3°C or a sustained temperature of $\geq 38^\circ\text{C}$ for more than one hour) and grade 3 or 4 thrombocytopenia with clinically significant bleeding will be dose limiting. Grade 3 non-hematologic toxicities except for nausea, emesis or diarrhea that are controlled with maximal medical management within 72 hours will be considered dose-limiting. DLTs will only be monitored during the first 6 weeks of treatment. Ongoing toxicity that causes a delay of more than 2 weeks in starting the next cycle will also be dose-limiting if it occurs during the first cycle.

Dose Modification and Escalation

Every effort should be made to administer the full dosing regimen of Ra-223 dichloride. Adjustment of dose level is not permitted.

- A minimum of 3 patients initially will be enrolled at the first dose level.
- If at least 2 patients are observed to have a dose-limiting toxicity (DLT), the MTD will have been exceeded and no further patients will be enrolled at this dose level or at any higher dose level. The prior dose level is defined as the MTD (unless only 3 patients have been treated at that level, in which case it is the tentative MTD).
- If 0 of the 3 patients are observed to have DLT during the DLT assessment period, the dose level is escalated one step for the next cohort of 3 patients, and the process continues as above.

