- If exactly 1 of the 3 patients treated show DLT during the DLT assessment period, 3 additional patients are treated at the current dose level.
- If none of these additional 3 patients show DLT during the DLT assessment period, the dose level is escalated for the next cohort of 3 patients, and the process continues as above; otherwise, the prior dose level is defined as the MTD (unless only 3 patients have been treated at that level, in which case it is the tentative MTD).
- A tentative MTD becomes final when a total of 6 patients are treated with less than 2 showing DLT.
- If 2 of the first 3 patients have hematologic DLT, then next cohort will be dose level -1.

Study visits during the treatment period should occur at 4 weeks intervals (within a window of +/- 7 days). **Dosing delays** may be instituted under the following circumstances:

Disease progression:

The Investigator should delay cytotoxic chemotherapy, other systemic radioisotope, hemibody external radiotherapy or other investigational drug until the follow-up period. If such treatments have to be given during the treatment period, further study drug administrations must be discontinued. Patients with disease progression may continue other treatment at the Investigator's discretion.

Myelosuppression:

Treatment-related changes in hematology parameters may occur.

- Blood transfusion is acceptable between study drug administrations. Use of biologic response modifiers, such as G-CSF or GM-CSF, is allowed in the management of acute toxicity.
- If myeloid growth factors are required for the management of acute toxicity this event should be considered a DLT.

Gastrointestinal events:

Diarrhea should be treated as per local practice. A further dose of study medication should not be given before diarrhea is recovered to CTCAE v4.03 Grade 2 or baseline levels.

Nausea or vomiting should be treated as per local practice. A further dose of study medication should not be given before nausea or vomiting is recovered to CTCAE v.4.03 Grade 2 or baseline levels.

For any grade 3 hematologic toxicity for >14 days, study drug administrations must be discontinued (grade 4 events of anemia and neutropenia >7 days are dose-limiting).

Spinal Cord Compression:

If the patient experiences spinal cord compression during the treatment period, the patient should be treated for the event, and this will be considered disease progression.

Surgical Intervention:

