7.4.1.3 Assessments and documentation of adverse events

7.4.1.4 Reporting of serious adverse events

The definition of serious adverse events (SAEs) is given in Section 7.4.1.1.

Each serious adverse event must be followed up until resolution or stabilization, by submission of updated reports to the designated person. An isolated laboratory abnormality that is assigned grade 4, according to CTC definition, is not reportable as an SAE; unless the investigator assesses that the event meets standard ICH criteria for an SAE. CTC grade 4 baseline laboratory abnormalities that are part of the disease profile should not be reported as an SAE, specifically when they are allowed or not excluded by the protocol inclusion/exclusion criteria.

When required, and according to local law and regulations, serious adverse events must be reported to the Ethics Committee and Regulatory Authorities.

All serious and unexpected adverse events should be reported to MD Anderson IRB and Bayer within 24 hours. In the event of such an event, the investigator should refer to the Pharmacovigilance section of the contract for reporting procedures.

The Investigator may report serious adverse drug reactions (SADRs) using either:

An ADEERS form (Adverse Event Expedited Reporting System) available at <http://ctep.cancer.gov/reporting/adeers.html>

OR

A MedWatch form available at <http://www.fda.gov/medwatch/>

All reports shall be sent electronically to:

Electronic Mailbox: [contact]

[contact]

Address: Global Pharmacovigilance - USA
Mail only: Bayer HealthCare
[name]
[name]

Address: [name]
FDX or UPS only [name]

Reports for all Bayer products can also be phoned in via our Clinical Communications Dept:

[contact]

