7.4.1.5 Expected adverse events

For this study, the applicable reference document is the most current version of the investigator's brochure (IB) / summary of product characteristics.

Overview listings of frequent events that have occurred so far in the clinical development are shown in the current IB. If relevant new safety information is identified, the information will be integrated into an update of the IB and distributed to all participating sites.

The expectedness of AEs will be determined by the study physician according to the applicable reference document and according to all local regulations.

7.4.1.6 Adverse events of special safety interest:

Since radium 223 dichloride is eliminated in the feces, but is an alpha emitter, feces containing the radiopharmaceutical can be safely disposed of by flushing down the toilet. If however there is ever an incident of placing the subjects excreta in the food of another person and the radiopharmaceutical is ingested (e.g. an alpha particle emitting special sandwich), this should be reported to the principal investigator and the principal investigator or designate should then determine whether the oral ingestion poses any safety risk (probably not) using gamma camera imaging to quantitate whether any significant bone absorption has occurred.

Long-term growth monitoring (<18 years only)

Patients with growth potential (e.g. epiphysis has significant uptake on the screening $^{99m}\text{TcMDP}$ scan) will have yearly growth monitored (and compared to weight and height vs weight percentile) for age until age 21 or no significant change of height is seen for 2 consecutive years- whichever is first.

Any secondary malignancies or potential long-term (i.e. > 2 months) grade 3 or greater hematologic toxicities will also be reported to MD Anderson IRB and Bayer.

Survival data will be reported yearly as long as MD Anderson Cancer Center IRB continuing review and yearly IND reporting is done. Data concerning any expected unexpected or unusual bone toxicities (e.g. hardware failure, pathologic fracture of limb salvage bones) will be collected and reported annually.

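### Section 5.2.1 withdraws patients with progression or DLT from study procedures as well as treatment, which contradicts the SAE and late follow-up required elsewhere; MTD decisions are unaffected

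*Combined protocol and SAP*

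**What the plan says.** **Withdrawal.** Section 5.2.1 lists reasons for mandatory withdrawal from the trial, with the scope given as "treatment and procedures) for the following reasons". One bullet reads "Progressive disease and dose limiting toxicity (DLT)". It stands beside withdrawn consent, loss to follow-up and death. For aftercare the section says only: "Any subject removed from the trial will remain under medical supervision until discharge or transfer is medically acceptable". No status of off treatment but in follow-up is defined.

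**Objective and DLT rule.** Section 2.1 sets the primary objective: "Determine maximum tolerated or recommended dose of monthly Ra-223 dichloride", together with a comparison of safety and toxicity at 50, 75 and 100 kBq/kg. The DLT definition after Section 6.2.9 says "DLTs will only be monitored during the first 6 weeks of treatment". The escalation rules say "A tentative MTD becomes final when a total of 6 patients are treated with less than 2 showing DLT".

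**Data required after treatment.**
- Section 7.4.1.2.1: SAEs are captured until 30 days after the last dose and followed to recovery or stabilisation. The only exception is withdrawn consent. Related SAEs after day 30, including second cancers, are still reported.
- Section 7.4.1.6: yearly growth monitoring in patients under 18 with growth potential, second cancers, and grade 3 or higher hematologic toxicity lasting more than 2 months. It also says "Survival data will be reported yearly".
- Table 4 (Section 7.1.1): an end-of-study assessment one month after dosing (read here as after the last dose), with examination, scans, blood count, chemistry and bone markers.

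**The concern.** A site that follows Section 5.2.1 literally stops study assessments when a patient has a DLT or progresses. The later sections require data from the same patients and make no exception for them. Two sites, or one site at two times, could each comply with part of the protocol and collect different data.

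The missing data would not be random, because toxicity or progression is what causes them to be missing. Section 7.4 puts every dosed patient in the safety analysis, and the primary objective compares toxicity across doses of a drug meant for repeated monthly use. Duration and reversibility of marrow toxicity matter for that comparison, and they would be least well documented in the patients who had the toxicity.

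**Working it through.** No stated figure of the plan is at stake. The check is mainly textual, with a rough scale at the end.

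**1. Is the conflict real?**

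| Item | Section 5.2.1 after progression or DLT | Other section |
|---|---|---|
| SAE capture and follow-up | Procedures end | 7.4.1.2.1: continues; only withdrawn consent excepted |
| Growth, second cancers, long-term hematologic toxicity, survival | Procedures end | 7.4.1.6: required; no exception for withdrawn patients |
| End-of-study assessment | Procedures end | Table 4: one month after dosing |

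The distinction between stopping drug and leaving the study was available to the authors: the pregnancy note in Section 5.2.1 speaks of withdrawal from treatment with study drug. Progression and DLT are not given that status.

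**2. The word joining progression and DLT.** The bullet says *and*. Reading it as *or* is plausible, since Section 8.1 treats progression by itself as an off-study criterion, but it is not explicit. Either reading needs rewording.

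**3. Do MTD decisions change?** A level is passed with 0 of 3 DLTs, or with 1 of 3 followed by 0 of 3:

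P(escalate) = (1−p)³ + 3p(1−p)² × (1−p)³

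For an assumed p = 0.20: 0.512 + 0.384 × 0.512 = 0.709. Only the number of patients with a DLT enters. The DLT is scored first and withdrawal follows, so the result is 0.709 with or without that patient's later data.

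**4. Does SAE follow-up fill the gap?** In part. The expected DLT is hematologic, and Section 7.4.1.4 states "An isolated laboratory abnormality that is assigned grade 4, according to CTC definition, is not reportable as an SAE", unless the investigator judges that it meets ICH criteria. The DLTs that may fall outside SAE follow-up are:
- an asymptomatic grade 4 cytopenia that does not meet ICH criteria;
- use of myeloid growth factors for acute toxicity;
- a delay of more than 2 weeks in starting the next cycle.

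No section guarantees blood counts to recovery for these.

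**5. A direct clash on long-term toxicity.** Doses are 4 weeks apart, and a first-cycle delay of more than 2 weeks is a DLT: 4 + 2 = 6 weeks after dose 1. Section 6.2.2 withholds the next dose until hemoglobin, neutrophils and platelets recover to grade 2 or less. A grade 3 or higher fall in one of these that starts in cycle 1 and lasts over 2 months therefore becomes a DLT at about week 6, before it reaches 2 months. Section 5.2.1 then ends the procedures that would show the duration Section 7.4.1.6 asks for.

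**6. Scale, with assumed rates.** Table 1 anticipates 9 to 20 patients. Expected number = n × p, and P(at least one) = 1 − (1−p)ⁿ. These treat n as fixed and p as the same at every dose, so they are a guide only.

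| Assumed DLT rate | Expected, n = 9 | P(≥1), n = 9 | Expected, n = 20 | P(≥1), n = 20 |
|---|---|---|---|---|
| 10% | 0.9 | 61% | 2 | 88% |
| 20% | 1.8 | 87% | 4 | 99% |
| 30% | 2.7 | 96% | 6 | >99% |

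For progression, assume exponential times with a median of m months. By day 42 (42/30.4375 = 1.38 months) the proportion is 1 − 0.5^(1.38/m). This gives 38%, 21% and 15% for m = 2, 4 and 6, or 7.6, 4.3 and 2.9 of 20 patients. Later progression adds to these.

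**The case against.** The strongest reply is that this is loose drafting and not a decision to stop follow-up. Section 7.4.3 mentions an end-of-treatment visit, the disease-progression text under Dose Modification and Escalation mentions a follow-up period, and Section 10 mentions post-study follow-up. Section 7.4 says all safety observations are recorded, and yearly survival needs no study procedure. Some hematologic DLTs, such as neutropenia with fever or thrombocytopenia with bleeding, are not isolated laboratory values and may well qualify as SAEs. For grade 4 neutropenia over 7 days, the minimum duration is seen before the DLT is declared.

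Much of this stands, and it rules out three stronger readings that a reader might infer:
- *The MTD is compromised.* It is not, as step 3 shows. Progression without a DLT before week 6 leaves an incomplete DLT window, but Section 5.2.3 lets such patients be replaced. That is a separate matter.
- *All follow-up stops.* Section 7.4.1.2.1 continues for SAEs by its own terms.
- *Late visits would rescue the comparison of baseline with after dose 6.* A patient who stops after dose 2 never has an after-dose-6 value. A visit one month after the last dose is a different exposure point.

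The reply does not remove the contradiction. The follow-up period is nowhere defined, Section 5.2.1 is the operative rule for the patients concerned, and assessments outside the SAE system have no stated basis after withdrawal.

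**Conclusion.** The point holds as an inconsistency with consequences for data collection. Section 5.2.1, read literally with *or* for *and*, contradicts Sections 7.4.1.2.1 and 7.4.1.6 and cuts off the Table 4 end-of-study assessment. The loss is confined to that assessment, recovery data for DLTs that are not SAEs, and late safety and survival data. It weakens the safety and toxicity comparison in the primary objective and leaves dose-escalation and MTD decisions untouched.

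The number of patients affected cannot be taken from the documents. Under assumed DLT rates of 10% to 30%, 2 to 6 of a maximum of 20 would come under the rule for DLT, and more for progression. How many would actually lose data depends on whether sites follow Section 5.2.1 over the later sections, so these are counts of patients exposed to the rule and not of patients with missing data.

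**What to change.** Reconcile Section 5.2.1 with Sections 7.4.1.2.1 and 7.4.1.6 by separating end of study treatment from end of study follow-up:

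1. Leave the treatment-stopping rules as they are, and state whether the bullet means progression *and* DLT or either one.
2. State that patients who stop for progression or DLT keep the existing Table 4 end-of-study assessment, the SAE follow-up of Section 7.4.1.2.1 and the late follow-up of Section 7.4.1.6. Where the DLT is itself a delay beyond week 6, one month plus 7 days after the last dose has already passed, so say when the assessment is then done.
3. Reserve withdrawal from procedures for withdrawn consent, loss to follow-up and death.
4. Report values from patients who stop early as last-on-study values, not as after-dose-6 values.

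The cost is protocol wording and one already-planned visit that comes earlier. No new type of assessment is added. Some patients will decline the visit, and the number who do should be reported by dose level.
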